### 3.0 Protocol Synopsis

Study Summary					
Study Purpose	To determine the optimal bowel preparation regimen for Pure-Vu System procedures in patients indicate for colonoscopy procedure.				
Objective	The primary objective of this multicenter, prospective, randomized study is to evaluate the performance of Pure-Vu System in cleansing patients' colon who are indicated for a colonoscopy procedure using one of two different reduce bowel preparation regimes.in addition, the cecum intubation rate, time to cecum, total procedure time, and adverse event will be evaluated.				
Test and Comparator Procedures	Prep A	Prep B			
5 days prior procedure day					
No seedy food					
1 day prior procedure day					
Low residue diet;					
Spilt dose of 15 oz Magnesium Citrate + 39 oz of clear liquid		Spilt dose of 10 oz Magnesium Citrate + 32oz of clear liquid			
Procedure Day					
Clear-liquid diet up to 3 hours prior to the procedure					
Fasting (no food / liquids) start 3 hours prior to procedure time					
*At least 2 liter water per day during the preparation days.					

Document title:  Optimizing the Preparation Regime Prior to Colonoscopy Procedure with Pure-Vu System	Document No.  CL00042	Version  1.0	Page 8 of 61
---	------------------------------------	---------------------------	-----------------

Protocol Number	CL00042
Protocol Title	Optimizing the Preparation Regime Prior to Colonoscopy Procedure with Pure-Vu System Rev 1.0
Study Sponsor	Motus GI Medical Technologies, [name] [contact] [contact]
Sponsor Representative	[name] Director of Clinical Affairs
Study Type	Multicenter, prospective, randomized feasibility study
Study Product	Pure-Vu System
Study Phase	Post-market
IDE Number	K173392 Class II
Study Location	United States
Study Duration	Study period will last approx. 12 months
Study Design	Patients will be randomized to receive one of two bowel preparation regimens prior to colonoscopy with Pure-Vu procedure.
Planned Follow-Up	Telephone follow-up will be conducted at 2-3 working days post-procedure to assess subject well-being and capture any adverse events.
Subject Population	Subjects indicate for colonoscopy procedure

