### 6.1.1 Work Station (WS)

The WS controls the flow of gas (e.g. air) and water or saline to the Oversleeve device and the evacuation of fecal matter and fluids out of the body. The WS has four main functions:

- **Cleansing:** Creates an irrigation stream, which is a mixture of liquid (water or saline) and air into the colon to break up fecal matter. The irrigation of air and liquid (water or saline) is referred to as “cleansing jets”. The cleansing has three modes, high, medium and low with medium being the default setting. The physician can operate the system as per his clinical judgment. It is important to note that the evacuation function noted below is active during cleansing so that fluid is input and removed from the colon simultaneously.
- **Evacuation:** Removes fecal matter and fluids out of the colon. The evacuation function is active during the cleansing as previously noted and can also be used independently. During evacuation the system senses the pressure in the evacuation channel of the Oversleeve and if the pressure goes below pre-set limits will automatically reverse the flow to purge a potential blockage and then switch back to continue evacuation. The user also has the ability to manually purge the evacuation channel as well.
- **User interface:** Consists of actuators and indicators on the WS itself as well as a foot pedal to activate the main functions of the system so that users’ hands are free to manipulate the colonoscope in a standard fashion.

**Oversleeve** The Oversleeve is mounted on top of the colonoscope and is connected to WS via the WS Connector. The Add-on includes the following main components:

- **Tubing:** Six (6) tubes (2 Pebax and 4 PVC) that support the irrigation, evacuation and sensing functions of the system.
- **Cleansing and Evacuation head:** The Oversleeve’s distal part which contains irrigation ports, evacuation openings, and colon sensing port.

Document title:	Document No.	Version	Page 16 of 61
Optimizing the Preparation Regime Prior to Colonoscopy Procedure with Pure-Vu System	CL00042	1.0	

- Inner sleeve: This sleeve attaches the Oversleeve to the colonoscope along its length. This sleeve is inflated to allow the colonoscope to be inserted through it and then deflated to hold onto the colonoscope when it is navigated through the colon. The inner sleeve is also attached to the outer sleeve noted below on one side.

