### Study Flow chart

#### 9.1 Primary Endpoint

The primary endpoint is the rate of adequate cleansing level per subject evaluated by the BBPS scoring index pre- and post the cleansing operation.

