#### **11.1.2 Randomization**

Randomization in blocks will be applied for each site to allocate patients to one of two different bowel preparation regimens (Prep A versus Prep B). The study will utilize randomization in blocks using the standard envelope procedure, which will be applied in order to allocate patients into two arms:

- Group 1 - Will go through the Prep A procedure
- Group 2 - Will go through the Prep B procedure

The site randomization plan will be provided to the study coordinator prior the study start. No blinding is applicable in this study.

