#### **11.1.5 Colonoscopy procedure (Visit 2)**

##### Pre-Examination Procedures

- Verify eligibility checked and informed consent was obtained after explaining all risks, benefits, and alternatives to the candidate.
- Verify that the research assistant has collected completed diaries from the subject.
- Verify all background/clinical information, demographic and medical history was documented

Note: Subjects that did not take the bowel preparation or failed to complete the bowel preparation will not undergo the procedure and will be excluded from the study.

- Verify all connections and assembles are properly attached (see Instructions for Use)
- Verify device works properly (see Instructions for Use)
- Place and prepare the subject for the procedure as per standard colonoscopy.
- Perform a digital rectal exam as per standard colonoscopy, evaluate the adequate level of the preparation and start the colonoscopy procedure with the Pure-Vu System as per standard of care.

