### **12.3 Primary Endpoint Hypothesis Analysis**

The primary endpoint is the rate of adequate bowel cleansing level after the use of the Pure- Vu.

The rate of adequate cleansing level in each colon segment before and after use of Pure-Vu will be evaluated using the Boston Bowel Preparation Scale (BBPS).

A score of 0 - 3 will be given to each of the 3 segments of the colon (Descending, Transverse and Ascending).

Document title:	Document No.	Version	Page 30 of 61
Optimizing the Preparation Regime Prior to Colonoscopy Procedure with Pure-Vu System	CL00042	1.0	

BBPS scores will be rated by the endoscopist, on the basis of three segment scores summed for maximum score of 9, where:

- 0 = unprepared
- 9 = completely clean (in completed to Cecum procedures)

*An adequate cleansing procedure is defined as when all 3 colon segments are graded as 2 or 3.*

Chi-square or Fisher's exact test, as appropriate, will be performed in order to compare proportions of good or excellent cleansing level between the two preparation procedures.

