## 21.0 Appendixes C: Boston Bowel Preparation Scale

- ❖ **A:** Score 0- Unprepared colon segment with mucosa not seen due to solid stool that cannot be cleared.
- ❖ **B:** Score 1 - A portion of the mucosa of the colon segment is seen, but other areas of the colon segment are not seen well due to staining, residual stool, and/or opaque liquid.
- ❖ **C:** Score 2- A minor amount of residual staining, small fragments of stool, and/or opaque liquid are visible, but the mucosa of the colon segment are seen well.
- ❖ **D:** Score 3- The entire mucosa of the colon segment is seen well with no residual staining, small fragments of stool, or opaque liquid.

Document title:	Document No.	Version	Page 48 of 61
Optimizing the Preparation Regime Prior to Colonoscopy Procedure with Pure-Vu System	CL00042	1.0	

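### The protocol rules out blinding for everyone, although the endoscopist who gives the subjective cleansing score does not need to know the arm and nothing keeps it from them

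*Protocol*

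**What the plan says.** Protocol section 11.1.2 allocates patients to Prep A or Prep B by blocked envelopes within site, gives the site randomisation plan to the study coordinator, and ends: "No blinding is applicable in this study". No reason follows, and no other section provides a masked endoscopist or masked reader.

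The Synopsis (section 3.0) describes arms that share diet and device and differ in the volumes drunk. Prep A is "Spilt dose of 15 oz Magnesium Citrate + 39 oz of clear liquid"; Prep B is 10 oz with 32 oz.

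On the outcome, section 12.3 says "BBPS scores will be rated by the endoscopist" and counts a patient as adequate only if every one of the three segments is graded 2 or 3. Appendix C describes grade 1 as a segment where some mucosa is seen but "other areas of the colon segment are not seen well due to staining, residual stool, and/or opaque liquid". At grade 2 the mucosa is seen well despite minor residue.

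Appendix F, the form completed by the physician, carries the study arm (10 oz or 15 oz) and the prescribed prep alongside the BBPS fields.

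**The concern.** Declaring blinding not applicable treats the trial as if masking were impossible for everyone. It is impossible for the patient, who drinks a known volume. It is not evidently impossible for the person whose judgement produces the primary endpoint.

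The cut between grades 1 and 2 is a visual call, and a single segment graded 1 turns a patient into a failure. A rater who knows the arm may, without intending to, grade borderline segments according to what they expect of the smaller or larger volume. At stake is the comparison of adequate-cleansing rates between the arms, which the protocol tests formally and, under section 12.7, means to use to judge whether Prep B tends to do better.

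**Working it through.** The protocol gives no figure on this point to reproduce. The check has two parts: who needs the arm and when, and how much room a biased rater would have.

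**Part 1. Who needs the arm**

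| Step | Role | Arm needed? |
|---|---|---|
| Allocation (11.1.2) | Coordinator holds the plan | Yes |
| Taking the prep (Synopsis) | Patient | Yes |
| Diary: "Verify that the research assistant has collected completed diaries from the subject" (11.1.5) | Research assistant | Will see it: the log in Appendix D records liquid volumes |
| Completion rule: "Subjects that did not take the bowel preparation or failed to complete the bowel preparation will not undergo the procedure" (11.1.5) | Whoever checks completion | Yes, but the result can be passed on as yes or no |
| BBPS on insertion and on withdrawal (11.1.5, 12.3) | Endoscopist | No |

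No step from the pre-examination checks to the end of the colonoscopy requires the endoscopist to have the arm in order to score. Appendix F does put the arm on the physician's form. Section 11.1.5 has the form completed after the procedure, however, so this shows only that the plan does not withhold the arm.

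**Part 2. Room for bias in the primary comparison**

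Inputs:
- Arm size 45 (up to 3 sites in the Synopsis × 15 per arm per site in section 9.0) or 50 (100 / 2).
- Earlier study, section 6.3, with a different (bisacodyl) prep: adequate in 25% before cleansing (95% CI 17% to 35%) and 99% after (94% to 100%); mean total BBPS 3.9 before and 8.7 after.
- Two-sided 0.05 is my assumption, because the protocol states no alpha.

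Results:
- One patient moved across the cut shifts an arm's rate by 1/45 = 2.2 points or 1/50 = 2.0 points.
- Expected inadequate after cleansing, per arm, at 99%: 0.01 × 45 = 0.45 or 0.01 × 50 = 0.50. At the lower limit of 94%: 0.06 × 45 = 2.7 or 0.06 × 50 = 3.0.
- Mean grade per segment: 3.9/3 = 1.3 before and 8.7/3 = 2.9 after. After cleansing, the average segment is well clear of the cut between 1 and 2.
- Fisher's exact test, 0 failures against k, equal arms of n: p = 2 × C(n,k) / C(2n,k).
  - n = 45: k = 5 gives 0.056; k = 6 gives 0.026.
  - n = 50: k = 5 gives 0.056; k = 6 gives 0.027.

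Starting from no failures in either arm, a rater would have to push six patients in one arm below the cut: 6/45 = 13.3% or 6/50 = 12.0%.

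Before cleansing the scores lie nearer the cut. The expected number adequate per arm is 0.25 × 45 = 11.25 or 0.25 × 50 = 12.5. Over the confidence interval it runs from 0.17 × 45 = 7.65 to 0.35 × 50 = 17.5. Section 9.1 has the endpoint "evaluated by the BBPS scoring index pre- and post the cleansing operation", but the Synopsis states the between-arm test for the post-cleansing proportion.

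**The case against.** The strongest reply is that this is an openly unpowered feasibility study whose tested endpoint is probably near its ceiling, so few borderline calls will arise. That stands and lowers the weight. It does not make blinding inapplicable: the protocol still plans a test on this score, and section 12.7 reads the direction of the result as informative.

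Second, masking will leak. The endoscopist sees the colon on insertion, and patients talk. That also stands. Imperfect masking would still remove direct disclosure of the arm.

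Third, the separation is not free. The investigator answers patients' questions at consent (11.1.1), may withdraw non-compliant subjects (10.3), and adverse events are collected from enrolment, hence during the prep (13.1). Where that investigator also performs the procedure, roles must really be divided.

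Fourth, examinations are recorded and archived (11.1.5), so a masked re-reading would be possible later. None is planned, so this mitigates the point without resolving it.

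A reader might also infer more than the protocol supports:
- *That the endoscopist knows the arm when scoring.* Appendix F does not show this, because it is filled in afterwards.
- *That procedure times are biased too.* Section 6.1.1 says "The physician can operate the system as per his clinical judgment", so an effect is possible. But cleanliness is visible on insertion, and cleansing effort would respond to it whether or not the arm is known.
- *That user ratings are biased.* The usability items in Appendix F are mainly mechanical (advancement, torque, retroflexion), and there is no clear reason why the prep volume would shift them.
- *That a false-positive rate can be attached.* This needs an assumed share of down-rated patients, for which the protocol gives no source.

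**Conclusion.** The point holds for assessor bias in BBPS scoring. The blanket statement in section 11.1.2 is not justified by the design, because the endoscopist has no need of the arm at scoring and the plan does nothing to withhold it. The bias is avoidable, but neither its size nor its direction can be derived from the protocol.

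If the 99% of the earlier study carries over, the room for bias in the tested post-cleansing rate is limited. If rates fall to 94% or lower under these preps, there is more room. Any effect on procedure times or user ratings is possible only. This is a worthwhile, low-cost improvement to a feasibility study and does not invalidate it. The figures rest on 45 to 50 patients per arm, a two-sided 0.05 level and an earlier study with a different prep.

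**What to change.** 1. Replace the sentence in section 11.1.2 with: *Patients are not blinded. The endoscopist is kept unaware of the assigned arm until the pre- and post-cleansing BBPS are recorded, unless the patient's care requires it.*
2. Move the study-arm and prescribed-prep fields of Appendix F to a page that the coordinator completes.
3. Have the coordinator open the envelope and give the prep instructions. The coordinator or research assistant keeps the diary until the scores are recorded and tells the endoscopist only yes or no on prep completion.
4. Ask patients and anyone else in the room, including the sponsor's representative who may attend, not to disclose the volume.
5. Where masking is not feasible or fails, record this, and list unmasked scoring as a limitation in section 12.7, which does not mention it now.

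The cost is a handful of procedural changes using the coordinator and research assistant already named in the protocol, with no added visit or reader. The real burden falls on sites where the investigator who consents patients or handles adverse events during the prep also performs the colonoscopy. Masking there needs a division of roles and may sometimes fail.

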#### **11.1.3 Screen Failures**

A subject is considered enrolled in the study when the ICF is signed. Only subjects who receive study-assigned procedures will be followed. Subjects who provide study consent, but then are determined to be ineligible prior to randomization will be considered screening failures and will

Document title:	Document No.	Version	Page 27 of 61
Optimizing the Preparation Regime Prior to Colonoscopy Procedure with Pure-Vu System	CL00042	1.0	

not require additional study follow-up. The reason for the screening failure will be clearly documented, the Subject "Enrollment and Visit Log" will be completed and the subject eligibility section in visit 1 as well as a "Study Completion" form will be completed in the CRF.

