## 9.0 Study Design

This multicenter, prospective, randomized study will include up to 100 patients (30 patients per site and 15 patients per study arm), aimed at evaluating the performance of Pure-Vu System in cleansing patients' colon who are indicated for colonoscopy procedure using one of two different preparation regimes as detailed below.

[figure not shown]
Subjects will be enrolled at up to 10 clinical sites in the United States. Subjects who meet the eligibility criteria will be randomly allocated to a given study arm and will be required to follow a specific bowel preparation instruction along with a specific prep agent (Bowel preparation instructions for morning and afternoon procedures are provided in appendix B1 and B2, respectively), as per study arm allocation, starting 5 days prior to the colonoscopy with Pure-Vu. Patients will be asked to record and provide their diet and bowel movements in the provided diary log at time of their scheduled colonoscopy (Diary log is provided in appendix D).

In addition patient will be asked to complete a satisfaction questionnaire include feedback on the procedure and on specific aspects related to the preparation regime.

Following the procedure a telephone follow-up will be conducted at 48 hours ( $\pm$  48 hours) post Pure-Vu procedure to assess patient well-being and capture any adverse events.

Document title:	Document No.	Version	Page 22 of 61
Optimizing the Preparation Regime Prior to Colonoscopy Procedure with Pure-Vu System	CL00042	1.0	

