### Post-Examination Follow-up

Subjects will be transferred to recovery room for observation per standard colonoscopy protocol. Subjects will be contacted by phone 2 working days after the procedure to verify that there has been no change in their well-being. Any AE will be documented in the CRF.

In addition questions about the patients' satisfaction with the Pure-Vu procedure will be completed.

Document title:	Document No.	Version	Page 29 of 61
Optimizing the Preparation Regime Prior to Colonoscopy Procedure with Pure-Vu System	CL00042	1.0	

Before a subject is considered “lost to follow-up”, there must be at least two documented attempts to contact the subject.

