## 12.4 Effectiveness Analyses

### Safety Analysis

The secondary endpoint is to evaluate the Device related adverse event and the overall adverse events rate. The safety analysis set will consist of all patients who were enrolled into the study.

Individual listings of adverse events including type of device, adverse events (reported term), seriousness, duration, relationship to the study device, severity and the adverse events outcome will be provided for the total population and per study arm. AEs will be summarized using frequency counts and percentages per study arm.

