## **12.5 Analysis Populations**

Cases withdrawn prior to the Pure-Vu procedure and those with technical failure will be excluded from the efficacy analysis. All patients who undergo bowel preparation will be included in the safety analysis.

Individual listings of withdrawal / failure including descriptive information will be provided.

In addition, in cases of incomplete procedure (i.e., the entire colon is not visualized); the overall BBPS per patient will be evaluated based on the colon segments that were visualized.

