### 13.1 Adverse Event (AE)

An AE is any untoward medical occurrence, unintended disease or injury, or untoward clinical signs (including abnormal laboratory findings) in subjects, whether or not related to the investigational medical device.

This definition includes events related to the investigational medical device or the comparator and the procedures involved.

AEs will be collected starting from the time subject is enrolled until the follow-up period is completed.

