## 19.0 Appendixes A: Study Design and Schedule of Assessment

Visit	Visit 1	Colon Preparation	Visit 2	Contact
Days	>-5 days	-1 to 0 days	0	48 hours
Informed Consent*	X			
Eligibility assessment (medical records, BMI, etc.)	X			
Randomization	X			
Colon Preparation Instructions	X			
Medical History, Concomitant Medications, Demographic details	X			
Diaries	X (providing)	X (by the patients)		
Patients' satisfaction questionnaire	X (providing)	X	X	
Bowel Preparation		X (by the patients)		
Colonoscopy Procedure			X	
Follow Up			X	X
Adverse Events Reporting			X	

Document title:	Document No.	Version	Page 45 of 61
Optimizing the Preparation Regime Prior to Colonoscopy Procedure with Pure-Vu System	CL00042	1.0	

[figure not shown]

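### Subjects who start but do not finish the bowel preparation stay in the safety analysis, yet no adverse event contact is scheduled for them after exclusion

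*Protocol*

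**What the plan says.** **Exclusion.** The note under Pre-Examination Procedures in section 11.1.5 covers subjects who "failed to complete the bowel preparation will not undergo the procedure and will be excluded from the study".

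**Follow-up contact.** Section 9.0 places the telephone call "post Pure-Vu procedure to assess patient well-being and capture any adverse events". Post-Examination Follow-up in section 11.1.5 reads "Subjects will be contacted by phone 2 working days after the procedure". The planned follow-up entry in the synopsis is also counted from the procedure. Section 11.1.3 states "Only subjects who receive study-assigned procedures will be followed".

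**Safety set.** Section 12.5: "All patients who undergo bowel preparation will be included in the safety analysis". The Safety Analysis paragraph of section 12.4 is wider: "The safety analysis set will consist of all patients who were enrolled into the study". Under section 11.1.3, enrolment means a signed consent form.

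**AE window.** Section 13.1: "AEs will be collected starting from the time subject is enrolled until the follow-up period is completed". Section 13.10 monitors an event until the subject completes the study, and longer only if the event is judged device-related.

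**Schedule.** In Appendix A, as it could be read, the row "Adverse Events Reporting" has a single mark, apparently under Visit 2.

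**The concern.** A subject who drinks part of the preparation and stops belongs to the safety set under either definition. Once excluded, that subject has no procedure date, so the call has nothing to be timed from and the follow-up period in section 13.1 has no defined end.

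The gap matters because the preparation is what is randomised. The synopsis gives both arms the same diet and device and varies the volumes of magnesium citrate and clear liquid. Section 5.1 names comparison of AE rates after the two preparations as a study objective, and section 12.4 reports AEs by arm. Section 7.2 expects nausea, vomiting, abdominal pain and dehydration from the preparation. The background in section 5.1 attributes non-completion to taste and to not tolerating the volume. Missing AE information is therefore plausibly related both to having an event and to the assigned arm.

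**Working it through.** The protocol states no AE rate, and section 12.1 gives the sample size no statistical basis, so there is no figure to reproduce. The check has two parts.

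**1. A subject who took some preparation, did not finish it and had no procedure**

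| Question | Source | Answer |
|---|---|---|
| In the safety set? | 12.4, 12.5 | Yes, under both definitions |
| Still in the study? | 11.1.5 note | No |
| AE recordable at Visit 2, if attended? | 13.1, 13.10, AE form in Appendix F | Yes |
| Follow-up call scheduled? | Synopsis, 9.0, 11.1.5 | No; each is counted from the procedure |
| End of AE collection defined? | 13.1 | No; it depends on a follow-up period the subject does not have |
| Monitoring of an ongoing event after exclusion? | 13.10 | Not provided for; the longer rule is for device-related events, and this subject never met the device |
| Symptoms captured by the diary? | Appendix D | No symptom field in the logs shown (meals, liquids, bowel movements) |

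Two groups of events therefore have no scheduled ascertainment: those in non-completers who do not attend Visit 2, and those that start or continue after exclusion.

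**2. Illustrative size**

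All inputs are assumptions. Let q be the non-completion rate, a_c the AE rate in completers and a_n the AE rate in non-completers.

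- True rate = (1 − q)·a_c + q·a_n
- Captured rate over the full safety set, if no non-completer event is recorded = (1 − q)·a_c
- Share of events lost = q·a_n / true rate

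With q = 10% and a_c = 10%:

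- a_n = 30%: true rate 0.90 × 0.10 + 0.10 × 0.30 = 12%; captured 0.90 × 0.10 = 9%; lost 0.03/0.12 = 25%.
- a_n = 50%: true rate 0.09 + 0.10 × 0.50 = 14%; captured 9%; lost 0.05/0.14 = 36%.

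Share of events lost for other values of q, with a_c = 10%:

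| q | a_n = 10% | a_n = 30% | a_n = 50% |
|---|---|---|---|
| 5% | 5% | 14% | 21% |
| 10% | 10% | 25% | 36% |
| 20% | 20% | 43% | 56% |

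If non-completion differs by arm, say 20% against 10% with a_n = 50%, the true rates are 0.08 + 0.10 = 18% and 0.09 + 0.05 = 14%, a difference of +4 points. The captured rates are 8% and 9%, a difference of −1 point.

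Every figure assumes that no non-completer event is captured. For the given rates, each is therefore an upper bound on the loss.

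**The case against.** Much of the AE machinery does reach these subjects. Collection starts at consent (13.1), all observed AEs are recorded whatever their severity or device relationship (13.10), and the AE form asks about the whole study. The completion check is made within Visit 2, so a non-completer who attends is in front of staff and can report an event. Reasons for withdrawal go into the CRF (10.3), withdrawals are listed individually (12.5), and the CRF records completion by regimen. All of this stands, and it limits the gap to non-attenders and to later or continuing events.

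A reader might infer from section 11.1.3 that follow-up is refused to non-completers. The text does not establish that. The sentence sits among the screen-failure rules, and section 11.1.2 calls each regimen a procedure, so someone who took preparation may count as having received one. The point rests on the exclusion note and the procedure-timed calls instead.

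A reader might also infer that all preparation AEs in non-completers are lost, with a large distortion. For example, at 5–20% non-completion, with 5% AEs in completers and an event in every non-completer, the true rate is 9.8–24% against 4.0–4.8% captured. That requires every non-completer to have an AE and none to be recorded, and the documents support neither. Disliking the taste or volume is not in itself an AE. The 38% non-completion in section 5.1 is a general background figure, not one for these reduced regimens. The Appendix A mark was read from an extracted table and proves little alone.

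Finally, section 8.2 frames safety around the device, AEs are summarised without a planned test, and the study is an unpowered pilot. That lowers the stakes. It does not remove the stated aim of comparing AE rates between the preparations.

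**Conclusion.** The concern holds in a limited form. The protocol keeps preparation non-completers in the safety analysis, excludes them from the study, and schedules no AE contact for them after exclusion. The AE rate per arm may be biased low, and differently by arm if non-completion differs. That non-completers have more AEs is an inference from the stated reasons for non-completion; the protocol gives no rate for them.

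The illustration of 12–14% true against 9% captured rests on assumed rates and on no capture at Visit 2, so the actual loss should be smaller wherever non-completers attend and report. The documents do not show that these events are generally lost or that these subjects have no safety contact at all. Follow-up contacts are set by the protocol, so this is not a detail to leave to a statistical analysis plan.

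**What to change.** In section 11.1.5, state that every randomised subject who took any of the preparation receives the AE follow-up call, timed from the planned procedure date if no procedure is done, and is analysed for safety in the assigned arm. Clarify in section 11.1.3 that these subjects are among those followed. State in the exclusion note that exclusion does not end AE collection.

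Reconcile the two safety-set definitions in sections 12.4 and 12.5, define in section 13.1 when follow-up ends for a subject without a procedure, and align the AE row of Appendix A so that it covers the preparation phase, Visit 2 and the contact.

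The cost is protocol wording and a few extra phone calls. The AE rate may look less favourable. No change is proposed to who undergoes the procedure or to either regimen.
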